10.7. Central Laboratory Testing

Biomarkers and Pharmacokinetic Sampling – At select study sites with the requisite experience and infrastructure for timed specimen collection, processing, storage and shipping, we will carry out baseline and timed measurements of Vitamin C (ascorbate), thiamine and cortisol, in order to characterize the relationship between these substances to disease severity, progression of disease and response to treatment. We will also assess baseline levels and pharmacokinetics of varied biomarkers associated with sepsis progression and response to therapy, in order to define the clinical utility of these biomarkers in the context of the TP. Sepsis biomarkers to be assessed will include complete blood count with differential, serum lactate, procalcitonin, C-reactive protein, and F2 isoprostane (a reliable sensitive biomarker of oxidative stress).

See table below. Initial blood and urine samples will be obtained after informed consent but prior to first study drug or placebo administration. The second sample collection will occur 30 minutes after completion of the first dose of study drugs or placebos. Subsequent sample collections will occur daily while in the ICU up to calendar day 4. The time of the daily specimen collection may be determined by the site research team, but these collections should occur at approximately the same time each day and within 90 minutes prior to the scheduled administration of study drug.

Collection Timepoint		Timing Description
1	1	After randomization, BEFORE any study drug administration
2	1 or 2	30 minutes after 1 st administration of all 3 study drugs is complete
3	2	Immediately prior to administration of study drugs
4	3	Immediately prior to administration of study drugs
5	4	Immediately prior to administration of study drugs

 Ψ : *Calendar Day* does not correspond with the EDC study day data collection. In most cases, collection 1 and 2 will occur on the same calendar day, except in cases where first drug is administered at ~midnight. Collection 3 should always be performed on the calendar day after collection 1 to prevent collection of blood volume that exceeds 45 mL on any single calendar day.

Samples will be processed and stored initially on site and then shipped to a central biorepository at Johns Hopkins University School of Medicine. Specimens will be aliquoted for biomarker and pharmacokinetic studies related the VICTAS study. Samples will be analyzed both at Johns Hopkins University and collaborating laboratories. Additional aliquots will be stored for the purpose of future studies that may include exploratory or development-phase assays. All biospecimens collected will be de-identified and associated with the subject using the unique subject code. No genetics will be collected.

Explicit consent will be sought for collection and storage of biospecimens for use in this study and unrelated future studies. However, consent to contribute to the biorepository is not required for participation in other aspects of the VICTAS study.

11. Statistical Considerations

11.1. General Considerations

Unless otherwise specified, continuous variables will be summarized by randomized treatment group with the number of non-missing observations, mean, standard deviation, median, 25th and 75th percentile displayed. Categorical data will be summarized by randomized treatment group as counts and percentages. All summaries and analyses will be performed using data pooled across centers.

11.2. Power and Sample Size

The trial has a flexible sample size that will be determined adaptively using a "Goldilocks" strategy with an initial enrollment target of up to 500 subjects. Patients will be randomized in a 1:1 ratio to receive either the Treatment Protocol (TP) or Control Protocol (CP), plus standard of care treatment (hereafter referred to in a combined manner as the "Study Intervention" or "Intervention").

Our analytical approach maximizes the potential for the trial to detect benefit, if it exists, by powering the study to detect a moderate effect on the VVFD endpoint (described in further detail below), while also allowing the trial to stop early if a very large effect is observed on our secondary outcome of mortality. This approach is desirable because an isolated study suggests a very strong effect on mortality (reference 20), yet clinical and research experience (references 18 and 19) suggest such a strong mortality benefit is unlikely and that more modest, but clinically meaningful, effects will be observed. Since we cannot preclude the possible large mortality benefit, we will check for it at the earliest adaptations. If the very large effect on mortality is not observed, we will continue enrollment with frequent interims that may stop the trial for benefit on VVFD. We will perform early interim analyses of the mortality endpoint when N=200, 300, and 400 subjects are enrolled. The trial may stop accrual if sufficiently robust results are observed on mortality at these interim analyses. If accrual is stopped in this way at any point, enrolled patients complete the study protocol for all outcome assessments and the primary analysis will be conducted with the complete data (see section 6: Study Design for additional details)..

Using a conservative estimate of the potential mortality difference of 20%, compared to the 32% mortality difference observed by Marik, et al.²⁰, the study has a power exceeding 90% in a one-sided test of proportions with alpha = 0.001. As such, the study is highly powered and very likely to stop at one of the interim analyses if the 20% treatment effect is real. If a more moderate treatment effect applies, the trial is more likely to continue beyond 500 subjects and would achieve lower power for the mortality endpoint. If the data are indeterminate on mortality after enrolling 400 patients, the trial may continue to a larger sample size (up to 2000).

For the primary outcome measure (VVFD), we will use an adaptive strategy with assessments at 500, 1000, 1500, or 2000 subjects randomized to either the TP or CP. When the data are sufficiently strong on the primary endpoint (VVFD), the trial may select a smaller sample size, but when necessary (e.g. for a moderate effect), the trial may continue to a larger sample size.

The overall Type I error rate for the trial is controlled at 2.5%. The early interims at N=200, 300, 400 are designed to conservatively spend alpha so that 2.4% remains for the analysis at N=500 (or beyond).

Anticipated alpha expenditures at all interim analyses, determined through clinical trial simulation, are as follows:

Interim Analysis	Alpha Spend
N = 200	0.0002
N = 300	< 0.0001
N = 400	0.0003
N = 500	0.010
N = 1000	0.0026
N = 1500	0.0033

The power estimates used for sample size selection if the trial progresses to N=500 and beyond were also determined through clinical trial simulation, and take into account both the primary outcome of VVFD and the secondary mortality outcome. Indeed, these two outcomes are inter-related, with our primary efficacy endpoint (VVFD) representing a combination of treatment effect on mortality (all deaths are recorded as zero VVFD) and effect on vasopressor and ventilator support dependence in survivors. Full details of these simulations, over a wide range of assumptions, may be found in a separate document entitled *VICTAS Trial Adaptive Design Report*.

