6.1. Design Overview

The VItamin C, Thiamine And Steroids in Sepsis (VICTAS) Study is a double-blind, placebo-controlled, adaptive randomized clinical trial designed to investigate the efficacy of the combined use of vitamin C, thiamine and corticosteroids (hereafter "Treatment Protocol" or "TP") versus indistinguishable placebos (hereafter "Control Protocol" or "CP") for patients with sepsis. The trial employs a novel endpoint that approximates a patient's risk of death based on the time spent on vasopressors or receiving respiratory support. Time spent on vasopressors or receiving respiratory support captures a patient's speed of recovery. Mortality rate is a key secondary endpoint for the trial.

The trial has a flexible sample size that will be determined adaptively. The trial will have an initial enrollment target of up to 500 subjects to detect a potential mortality difference of 20%, a conservative estimate based on the 32% benefit observed in the study by Marik, et al. However, if the data are indeterminate on mortality at N=200, 300, or 400 subjects, the trial may continue to a larger sample size (up to 2000) using an adaptive "Goldilocks" strategy based on the primary endpoint of VVFD with assessments at 500, 1000, 1500, or 2000 subjects randomized to either the TP or CP. The overall type I error rate for the trial is controlled at 2.5%. The early interim analyses have conservative rules for spending alpha so that 0.1% will be used up to N=400 and the remaining 2.4% is reserved for N=500 (or beyond). For more detail, please see section on Statistical Considerations below (Section 11).

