6.2. Interim Analyses and Criteria for Study Termination

Early interim analyses focused on detection of a large mortality effect will be conducted as soon as possible following the enrollment of subject numbers 200, 300, and 400. At each of these points, predictive probability of meeting significance on the endpoint of mortality once all currently enrolled subjects have been followed to their final outcome will be calculated. If predictive probability of achieving statistical significance (with one-sided alpha set at 0.001) exceeds 90%, study accrual will be stopped. All currently enrolled subjects will continue and the final analysis will be conducted after all currently enrolled subjects have been followed to their final outcome.

If these conditions are not met, the trial will continue under an adaptive "Goldilocks" strategy with a primary endpoint of VVFD. Interim analyses under this design will be performed as soon as possible following the enrollment of subject numbers 500, 1000 and 1500. Following each of these interim analyses, any one of the following actions may result:

- a. Stoppage of the trial for futility on VVFD (6.2.a)
- b. Stoppage of accrual for expected success on VVFD and mortality (6.2.b)
- c. Stoppage of accrual for expected success on VVFD alone (6.2c)
- d. Continuation to the next analysis (6.2.d)

The decision criteria are based on predictive probabilities of meeting statistical significance on VVFD or mortality. Thus, we compute the predictive probability that VVFD (and mortality) will meet statistical significance once all currently enrolled subjects have been followed to their final outcome (30 days after

enrollment). We also compute the predictive probability that VVFD (and mortality) will be significant if the trial continues to its maximum sample size of N=2000. Each of the possible interim actions is described in greater detail below.

a.) Stoppage of the trial for futility

Stoppage of the trial for futility will occur if there is less than 10% predictive probability of ever detecting a statistically significant (alpha = 0.022) beneficial effect on VVFD, even if enrollment continues to 2000 subjects.

b.) Stoppage of accrual for expected success on both VVFD and mortality.

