11.4. Final Data Analysis

The final data analysis will be performed after all enrolled subjects have completed follow up. If the trial stops for expected success on the mortality endpoint at N=200, 300, or 400, the final analysis will be based solely on mortality and will require p<0.001. If the trial reaches N=500 or more without predicted success on mortality, indicating more moderate effects, the primary analysis will be based on the more sensitive VVFD endpoint using the remaining 2.4% alpha.

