11.4.1. Primary Efficacy Endpoint

The primary efficacy endpoint is vasopressor and ventilator-free days (VVFD) in the first 30 days after start of treatment. The endpoint will be recorded to the nearest day. Subjects who die will be scored zero days, even if there is a period during which the subject is alive and free of vasopressors and mechanical ventilation. Subjects who must return to ventilation and/or vasopressors will have their counters reset at zero days. If the trial reaches N=500 or more, the primary analysis is a Wilcoxon rank-sum test (also known as a Mann-Whitney U test), which will be performed using a one-sided alpha of 0.022. If the study is extended beyond N=500, then the final analysis on VVFD requires p<0.022. This p-value threshold was selected through simulations in order to control type I error and account for the multiple analyses at N=500, 1000, 1500 and 2000.

The primary analysis will be performed on the ITT population. A sensitivity analysis will be performed on the PP analysis set.

For subjects with missing data on the primary endpoint, a "last status carried forward" approach will be used. If a subject was last seen on either vasopressors or mechanical ventilation, it is assumed that the subject remained so, and is imputed to a value of zero VVFD. If the subject was last seen off of vasopressors and mechanical ventilation and is not known to be dead, it is also assumed that the subject remained so in the remainder of the 30-day period.

VVFDs will be tabulated by arm and presented graphically by histograms and cumulative distribution functions.

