11.5.1. Statistical Models for the Interim Analysis

At the time of each interim analysis, there will be subjects for whom the final outcome is unknown (e.g. subjects who are enrolled but whose data is not yet available, or future subjects not yet enrolled). To make decisions regarding sample size selection, Bayesian predictive distributions are employed for the multiple imputation of outcomes for such subjects. These models will play no role in the final analysis, but rather are only used to facilitate the early stopping rules at the interims.

Predictive Probabilities for Mortality

To compute predictive probabilities for the mortality endpoint alone, we rely on a Beta-Binomial model, with independent non-informative Beta(0.5, 0.5) priors on each q_j , where q_j is the mortality rate on arm j. Based on this model, we compute:

- PP_{mort} (current N): the predictive probability of success on the mortality endpoint (Chi square test) if enrollment stops at the current sample size, and all currently enrolled subjects are followed to their primary outcome.
- PP_{mort} (max N): the predictive probability of success on the mortality endpoint (Chi square test) if enrollment continues to the maximum sample size (N=2000), and all subjects are followed to their primary outcome.

Similarly, we compute predictive probabilities for the VVFD endpoint using a model based on an exponential family (additional details of the model may be found in a separate document entitled *VICTAS Trial Adaptive Design Report*):

- PP_{VVFD} (current N): the predictive probability of success on the VVFD endpoint (Wilcoxon test) if enrollment stops at the current sample size, and all currently enrolled subjects are followed to their primary outcome.
- PP_{VVFD} (max N): the predictive probability of success on the VVFD endpoint (Wilcoxon test) if enrollment continues to the maximum sample size (N=2000), and all subjects are followed to their primary outcome.

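### The N=500 alpha-spend entry of 0.010 in section 11.2 does not fit the other rows, the p<0.022 final threshold and the 2.5% total

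*Combined protocol and SAP*

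**What the plan says.** - Section 6.1 gives the overall claim: "The overall type I error rate for the trial is controlled at 2.5" per cent. It assigns 0.1% to the looks up to N=400 and 2.4% to N=500 and beyond.
- Section 11.2 repeats the split, saying that the early looks "spend alpha so that 2.4% remains for the analysis at N=500 (or beyond"). It then prints simulated spends, introduced by "Anticipated alpha expenditures at all interim analyses, determined through clinical trial simulation, are as follows": 0.0002 (N=200), <0.0001 (N=300), 0.0003 (N=400), 0.010 (N=500), 0.0026 (N=1000) and 0.0033 (N=1500).
- Section 11.4 says that, once the trial reaches N=500, "the primary analysis will be based on the more sensitive VVFD endpoint using the remaining 2.4% alpha".
- Section 11.4.1 makes the Wilcoxon test one-sided and adds: "If the study is extended beyond N=500, then the final analysis on VVFD requires p<0.022". On its origin it says: "This p-value threshold was selected through simulations in order to control type I error", covering the analyses at 500, 1000, 1500 and 2000.
- Section 6.2 sets the futility rule: "Stoppage of the trial for futility will occur if there is less than 10% predictive probability" of VVFD significance even at 2000 subjects.
- Section 11.5.1 says of the interim model that "we compute predictive probabilities for the VVFD endpoint using a model based on an exponential family", with details in the separate Adaptive Design Report.

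**The concern.** The table is the only look-by-look support for the 2.5% claim. Its rows and the claimed total fix what can be left for N=2000, and section 11.4.1 fixes the test done there. If the residual and the test disagree, at least one printed figure is wrong, unless the unseen VVFD predictive model stops far more null trials for futility than an ordinary prior would.

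The consequence depends on which figure it is. A slip in one table entry affects no test. A threshold of 0.022 tuned under stopping rules other than those written would affect the primary analysis. A reader of the protocol cannot tell these apart.

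**Working it through.** **Inputs.** Rows, 2.5% and 2.4%: section 11.2. One-sided 0.022, so z = 2.014: section 11.4.1. Futility and success rules: sections 6.2 and 11.5.2. I read each row as the null probability of stopping accrual at that look and then winning. Normal approximations are used throughout.

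**1. What the rows leave.**
- All rows: 0.0002 + (<0.0001) + 0.0003 + 0.010 + 0.0026 + 0.0033 = 0.0164 to 0.0165. Left for N=2000: 0.025 − 0.0165 = 0.0085.
- VVFD rows: 0.010 + 0.0026 + 0.0033 = 0.0159. Left of the VVFD budget: 0.024 − 0.0159 = 0.0081.

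**2. A floor that needs no VVFD–mortality correlation.** Earlier successes reduce the 0.022 at N=2000 only where the success sets overlap. For a row of size a at look n, the largest overlap is P(Z_n > z_(1−a), Z_2000 > 2.014), with correlation √(n/2000).

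| Look | Row | Largest overlap |
|---|---|---|
| 500 | 0.010 | 0.0022 |
| 1000 | 0.0026 | 0.0015 |
| 1500 | 0.0033 | 0.0029 |

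The sum is 0.0066. Early mortality stops overlap by at most 0.0006.
- Without futility: 0.022 − 0.0066 − 0.0006 = 0.0148 at N=2000. Total at least 0.0165 + 0.0148 = 0.0313.
- With futility: the 10% rule under a flat prior removes 0.0029. Total at least 0.0313 − 0.0029 = 0.0284.

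Trials that stop for expected success and then fail the final test change this by only about 0.0001.

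**3. An estimate rather than a floor.** Hold the spends at 500, 1000 and 1500 to the printed values over 6 million null trials. Apply futility when Φ[(Z_n − 2.014√t)/√(1−t)] < 0.10, with t = n/2000.

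| N=500 row | Futility | Spend at N=2000 | VVFD looks in total |
|---|---|---|---|
| 0.010 | applied | 0.0130 | 0.0159 + 0.0130 = 0.0289 |
| 0.010 | none | 0.0159 | 0.0159 + 0.0159 = 0.0318 |
| 0.0010 | applied | 0.0146 | 0.0069 + 0.0146 = 0.0215 |
| 0.0010 | none | 0.0175 | 0.0069 + 0.0175 = 0.0244 |

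Adding 0.0005 for the early rows, a value of 0.0010 gives 2.2% to 2.5% overall. The stated 2.5% is not reproduced with 0.010. Pending counts of 14 to 80 hardly move the result. Reading 0.010 as a rounded 0.0095 gives 2.85% for the VVFD looks with futility.

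**4. How strong a prior would close the gap.** Reaching 2.5% from the floor needs 0.0313 − 0.025 = 0.0063 removed by futility. A null-centred prior worth 500 patients removes 0.0046 to 0.0048, and one worth 1000 removes 0.0063 to 0.0066. Even at 1000, the direct calculation gives about 2.57% for the VVFD looks alone.

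**5. What the written rules produce.** This simulates sections 6.2 and 11.5.2 (3 million null trials per setting, flat prior, futility applied). Correlation and pending counts are assumed. Planned accrual suggests about 500/36 = 14 or 20 × 2 = 40 pending for a 30-day outcome.

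| Correlation, pending | N=500 | N=1000 | N=1500 | Overall total |
|---|---|---|---|---|
| 0.7, 60 | 0.0015 | 0.0023 | 0.0032 | 0.0229 |
| 0.8, 60 | 0.0021 | 0.0030 | 0.0031 | 0.0237 |
| 0.7, 40 | 0.0020 | 0.0028 | 0.0038 | 0.0240 |
| 0.7, 14 | 0.0031 | 0.0040 | 0.0052 | 0.0269 |
| 0.88, 14 | 0.0057 | 0.0059 | 0.0050 | 0.0298 |
| Printed | 0.010 | 0.0026 | 0.0033 | 0.025 |

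Settings that come near the N=1000 and N=1500 rows put N=500 at about 0.002. Across all settings tried, N=500 lies at about 0.001 to 0.006. Dropping the mortality condition from the stopping rule gives 0.0117 with 14 pending and about 0.008 with 40, so 0.010 is reachable only under a rule that is not the one written.

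**The case against.** **The rows drive no decision.** Success depends on 0.022, 0.024, 0.001 and the predictive-probability cut-offs. This is right, and it matters for the strongest reading that a reader might take from the 2.9%: that the trial's true type I error exceeds 2.5%. The documents do not support that reading. The 2.9% follows only if 0.010 is correct. The written rules simulate on either side of 2.5%, depending on a correlation and a pending count that the protocol does not state, and the settings closest to the neighbouring rows give 2.3% to 2.4%.

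**It may be a dropped zero.** The other numeric rows have four decimals and this one has three. A lost zero, in the original or in text extraction, fits the arithmetic well. That cannot be proved from the text, so the entry still needs checking.

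**The detail is in the Adaptive Design Report.** The VVFD predictive model is there, and the flat prior here is a stand-in. Only the futility part depends on it; the 3.1% floor without futility does not. A separate report also cannot make figures printed in one section agree. Section 11.2 does mention a wide range of simulated assumptions, so rows drawn from different scenarios could not be summed. The table gives no sign of that, and the protocol would need to say so.

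**There is no N=2000 row.** This is not an error: the table covers interim analyses and N=2000 is the final one. Futility that the DSMB may recommend before N=500 could only lower the total, but it has no numerical criterion and cannot be credited.

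**Conclusion.** The printed figures do not fit together. With the rows as printed, the VVFD looks total about 2.9% with futility applied and 3.2% without, against 2.4% reserved. The overall floor is about 2.8% or 3.1%, against 2.5%. The futility-adjusted figures assume a flat predictive prior; a null-centred prior worth about 1000 patients would be needed to come close to 2.5%.

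The N=500 entry is the most likely error, because it lies above everything simulated under the written rules and 0.0010 would restore consistency. That is an inference: the documents do not settle whether the entry, the 0.022 or the 2.5% is wrong. Confidence is high for the mismatch and lower for its cause.

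**What to change.** Check the N=500 entry against the Adaptive Design Report and correct it. If it was a misprint, the cost is one lookup and one corrected cell, and no test changes.

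If 0.010 is what the simulation gave, re-run it under exactly the rules in section 11.5.2. If the total then exceeds 2.5%, restate the overall error rate or tighten the 0.022 VVFD threshold to the value that the simulation supports. Say also whether the 2.5% relies on futility stops being followed. At worst this means a slightly stricter threshold with a small loss of power, and no extra patients.
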